7.5.4 Management of Immune-Related Adverse Events

Since inhibition of PD-L1 stimulates the immune system, immune-related Adverse Events (AEs) may occur. Avelumab can result in severe and fatal immune-related adverse reactions. These immune-related reactions may involve any organ system. Most immune-related reactions initially manifest during avelumab treatment; however, immune-related adverse reactions can occur after discontinuation of avelumab.

Monitor patients for signs and symptoms of pneumonitis, colitis, changes in thyroid function, adrenal insufficiency, hyperglycaemia (or other signs and symptoms of diabetes), abnormal liver tests and elevated serum creatinine at the start of treatment and periodically during treatment.

Treatment of AEs is mainly dependent upon severity (NCI-CTCAE grade):

Grade 1 to 2: treat symptomatically or with moderate dose steroids, more frequent monitoring

Grade 1 to 2 (persistent): manage similar to high grade AE (Grade 3 to 4)

Grade 3 to 4: treat with high dose corticosteroids

Treatment of gastrointestinal, dermatological, pulmonary, hepatic, renal, endocrine and Cardiac AEs should follow guidelines set forth in the table below Table 4.

Table 4. Management of Immune-Related Adverse Events

Gastrointestinal AEs		
Severity of Diarrhea / Colitis (NCI-CTCAE v4.03)	Management	Follow-up
Grade 1 Diarrhea: < 4 stools/day over Baseline Colitis: asymptomatic	Continue avelumab therapy Symptomatic treatment (for example, loperamide)	Close monitoring for worsening symptoms Educate subject to report worsening immediately If worsens: Treat as Grade 2 or 3/4
Grade 2 Diarrhea: 4 to 6 stools per day over Baseline; IV fluids indicated < 24 hours; not interfering with ADL Colitis: abdominal pain; blood in stool	Withhold avelumab therapy Symptomatic treatment Treat Grade 2 colitis with 1.0 to 2.0 mg/kg/day prednisolone IV or equivalent	If improves to Grade 1: Resume avelumab therapy For Grade 2 colitis continue steroids until Grade 1, then taper over at least 1 month; resume Avelumab therapy following steroids taper. If persists > 5 to 7 days or recur: Treat as Grade 3 to 4
Grade 3 to 4 Diarrhea (Grade 3): ≥ 7 stools per day over Baseline; incontinence; IV fluids ≥ 24 hrs.; interfering with ADL Colitis (Grade 3): severe abdominal pain, medical intervention indicated, peritoneal signs Grade 4: life-threatening, perforation	Withhold avelumab for Grade 3. 1.0 to 2.0 mg/kg/day prednisolone IV or equivalent Add prophylactic antibiotics for opportunistic infections Consider lower GI endoscopy. Permanently discontinue avelumab for Grade 4 or recurrent Grade 3.	If improves: Continue steroids until Grade 1, then taper over at least 1 month; resume Avelumab therapy following steroids taper (for initial Grade 3). If worsens, persists > 3 to 5 days, or recurs after improvement: Add infliximab 5 mg/kg (if no contraindication), Note: Infliximab should not be used in cases of perforation or sepsis
Dermatological AEs		
Grade of Rash (NCI-CTCAE v4.03)	Management	Follow-up
Grade 1 to 2 Covering ≤ 30% body surface area	Symptomatic therapy (for example, antihistamines, topical steroids) Continue avelumab therapy	If persists > 1 to 2 weeks or recurs: Withhold Avelumab therapy Consider skin biopsy Consider 0.5 to 1.0 mg/kg/day prednisolone or equivalent. Once improving, taper steroids over at least 1 month, consider prophylactic antibiotics for opportunistic infections, and resume avelumab therapy following steroids taper. If worsens: Treat as Grade 3 to 4

Grade 3 to 4 Grade 3: Covering > 30% body surface area; Grade 4: life threatening consequences	Withhold avelumab for Grade 3. Permanently discontinue avelumab for Grade 4 or recurrent Grade 3. Consider skin biopsy Dermatology consult 1.0 to 2.0 mg/kg/day prednisolone or equivalent Add prophylactic antibiotics for opportunistic infections	If improves to Grade ≤1: Taper steroids over at least 1 month; resume Avelumab therapy following steroids taper (for initial Grade 3).
Pulmonary AEs		
Grade of Pneumonitis (NCI-CTCAE v4.03)	Management	Follow-up
Grade 1 Radiographic changes only	Consider withholding avelumab therapy Monitor for symptoms every 2 to 3 days Consider Pulmonary and Infectious Disease consults	Re-assess at least every 3 weeks If worsens: Treat as Grade 2 or Grade 3 to 4
Grade 2 Mild to moderate new symptoms	Withhold avelumab therapy Pulmonary and Infectious Disease consults Monitor symptoms daily, consider hospitalisation 1.0 to 2.0 mg/kg/day prednisolone or equivalent Add prophylactic antibiotics for opportunistic infections Consider bronchoscopy, lung biopsy	Re-assess every 1 to 3 days If improves: When symptoms return to Grade ≤1, taper steroids over at least 1 month and then resume avelumab therapy following steroids taper If not improving after 2 weeks or worsening: Treat as Grade 3 to 4
Grade 3 to 4 Grade 3: Severe new symptoms; New / worsening hypoxia; Grade 4: life-threatening	Permanently discontinue avelumab therapy Hospitalize Pulmonary and Infectious Disease consults 1.0 to 2.0 mg/kg/day prednisolone or equivalent Add prophylactic antibiotics for opportunistic infections Consider bronchoscopy, lung biopsy	If improves to Grade ≤1: Taper steroids over at least 1 month If not improving after 48 hours or worsening: Add additional immunosuppression (for example, infliximab, cyclophosphamide, IV immunoglobulin, or mycophenolate mofetil)
Hepatic AEs		
Inform the CI and trials office immediately if the treating investigator has concerns over liver function or liver involvement by lymphoma		
Grade of Liver Test Elevation (NCI-CTCAE v4.03)	Management	Follow-up
Grade 1	Continue avelumab therapy	Continue liver function

Grade 1 AST or ALT > ULN to 3.0 x ULN and / or total bilirubin > ULN to 1.5 x ULN		monitoring If worsens: Treat as Grade 2 or 3 to 4
Grade 2 AST or ALT > 3.0 to \leq 5 x ULN and / or total bilirubin > 1.5 to \leq 3 x ULN	Withhold avelumab therapy Increase frequency of monitoring to every 3 days 1.0 to 2.0 mg/kg/day prednisolone or equivalent	If returns to Grade \leq 1: Taper steroids over at least 1 month, : resume routine monitoring, resume avelumab therapy following steroids taper If elevations persist > 5 to 7 days or worsens: Treat as Grade 3 to 4.
Grade 3 to 4 AST or ALT > 5 x ULN and / or total bilirubin > 3 x ULN	Permanently discontinue avelumab therapy Increase frequency of monitoring to every 1 to 2 days 1.0 to 2.0 mg/kg/day prednisolone or equivalent Add prophylactic antibiotics for opportunistic infections Consult gastroenterologist / hepatologist Consider obtaining MRI/CT scan of liver and liver biopsy if clinically warranted	If returns to Grade \leq 1: Taper steroids over at least 1 month If does not improve in > 3 to 5 days, worsens or rebounds: Add mycophenolate mofetil 1 gram (g) twice daily If no response within an additional 3 to 5 days, consider other immunosuppressants per local guidelines
Renal AEs		
Grade of Creatinine Increased (NCI-CTCAE v4.03)	Management	Follow-up
Grade 1 Creatinine increased > ULN to 1.5 x ULN	Continue avelumab therapy	Continue renal function monitoring If worsens: Treat as Grade 2 to 3 or 4.
Grade 2 to 3 Creatinine increased > 1.5 and \leq 6 x ULN	Withhold avelumab therapy Increase frequency of monitoring to every 3 days 1.0 to 2.0 mg/kg/day prednisone or equivalent. Add prophylactic antibiotics for opportunistic infections Consider renal biopsy	If returns to Grade \leq 1: Taper steroids over at least 1 month, and resume avelumab therapy following steroids taper. If worsens: Treat as Grade 4.
Grade 4 Creatinine increased > 6 x ULN	Permanently discontinue avelumab therapy Monitor creatinine daily 1.0 to 2.0 mg/kg/day prednisone or equivalent. Add prophylactic antibiotics for opportunistic infections	If returns to Grade \leq 1: Taper steroids over at least 1 month.

	Consider renal biopsy Nephrology consult	
Cardiac AEs		
Myocarditis	Management	Follow-up
New onset of cardiac signs or symptoms and / or new laboratory cardiac biomarker elevations (e.g. troponin, CK-MB, BNP) or cardiac imaging abnormalities suggestive of myocarditis.	Withhold avelumab therapy Hospitalize. In the presence of life threatening cardiac decompensation, consider transfer to a facility experienced in advanced heart failure and arrhythmia management. Cardiology consult to establish etiology and rule-out immune-mediated myocarditis. Guideline based supportive treatment as appropriate per cardiology consult.* Consider myocardial biopsy if recommended per cardiology consult.	If symptoms improve and immune-mediated etiology is ruled out, re-start avelumab therapy. If symptoms do not improve/worsen, viral myocarditis is excluded, and immune-mediated etiology is suspected or confirmed following cardiology consult, manage as immune-mediated myocarditis.

*Local guidelines, or eg. ESC or AHA guidelines

ESC guidelines website:

<https://www.escardio.org/Guidelines/Clinical-Practice-Guidelines>

AHA guidelines website:

<http://professional.heart.org/professional/GuidelinesStatements/searchresults.jsp?q=&y=&t=1001>

Endocrine AEs		
Endocrine Disorder	Management	Follow-up
Grade 1 or Grade 2 endocrinopathies (hypothyroidism, hyperthyroidism, adrenal insufficiency, type I diabetes mellitus)	Continue avelumab therapy Endocrinology consult if needed Start thyroid hormone replacement therapy (for hypothyroidism), anti-thyroid treatment (for hyperthyroidism), corticosteroids (for adrenal insufficiency) or insulin (for Type I diabetes mellitus) as appropriate. Rule-out secondary endocrinopathies (i.e. hypopituitarism / hypophysitis)	Continue hormone replacement / suppression and monitoring of endocrine function as appropriate.

Grade 3 or Grade 4 endocrinopathies (hypothyroidism, hyperthyroidism, adrenal insufficiency, type I diabetes mellitus)	Withhold avelumab therapy Consider hospitalisation Endocrinology consult Start (as appropriate): 
 thyroid hormone replacement therapy for hypothyroidism anti-thyroid treatment for hyperthyroidism, corticosteroids for adrenal insufficiency anti-hyperglycemics or insulin for type I diabetes mellitus Rule-out secondary endocrinopathies (i.e. hypopituitarism / hypophysitis)	Resume avelumab once symptoms and / or laboratory tests improve to Grade ≤ 1 (with or without hormone replacement / suppression). Continue hormone replacement / suppression and monitoring of endocrine function as appropriate.
Hypopituitarism/Hypophysitis (secondary endocrinopathies)	If secondary thyroid and / or adrenal insufficiency is confirmed (i.e. subnormal serum FT4 with inappropriately low TSH and/or low serum cortisol with inappropriately low ACTH) : 
 Refer to endocrinologist for dynamic testing as indicated and measurement of other hormones (FSH, LH, GH/IGF-1, PRL, testosterone in men, estrogens in women) Hormone replacement/suppressive therapy as appropriate Perform pituitary MRI and visual field examination as indicated If hypophysitis confirmed: 
 Continue avelumab if mild symptoms with normal MRI. Repeat the MRI in 1 month Withhold avelumab if moderate, severe or life-threatening symptoms of hypophysitis and / or abnormal MRI. Consider hospitalisation. Initiate corticosteroids (1 to 2 mg/kg/day prednisone or equivalent) followed by corticosteroids taper during at least 1 month. Add prophylactic antibiotics for opportunistic infections. 	Resume avelumab once symptoms and hormone tests improve to Grade ≤ 1 (with or without hormone replacement). In addition, for hypophysitis with abnormal MRI, resume Avelumab only once shrinkage of the pituitary gland on MRI/CT scan is documented. Continue hormone replacement / suppression therapy as appropriate.
Other AEs (not described above)		
Grade of other AEs (NCI-CTCAE v4.03)	Management	Follow-up
Grade 2 or Grade 3 clinical signs or symptoms suggestive of a potential immune-related	Withhold avelumab therapy pending clinical investigation	If irAE is ruled out, manage as appropriate according to the diagnosis and consider re-

AE (irAE)		starting avelumab therapy If irAE is confirmed, treat as Grade 2 or 3 irAE.
Grade 2 irAE or first occurrence of Grade 3 irAE	Withhold avelumab therapy 1.0 to 2.0 mg/kg/day prednisone or equivalent Add prophylactic antibiotics for opportunistic infections Specialty consult as appropriate	If improves to Grade \leq 1: Taper steroids over at least 1 month and resume avelumab therapy following steroids taper.
Recurrence of same Grade 3 irAEs	Permanently discontinue Avelumab therapy 1.0 to 2.0 mg/kg/day prednisone or equivalent Add prophylactic antibiotics for opportunistic infections Specialty consult as appropriate	If improves to Grade \leq 1: Taper steroids over at least 1 month
Grade 4	Permanently discontinue Avelumab therapy 1.0 to 2.0 mg/kg/day prednisone or equivalent Add prophylactic antibiotics for opportunistic infections Specialty consult as appropriate	If improves to Grade \leq 1: Taper steroids over at least 1 month
Requirement for 10 mg per day or greater prednisone or equivalent for more than 12 weeks for reasons other than hormonal replacement for adrenal insufficiency Persistent Grade 2 or 3 irAE lasting 12 weeks or longer	Permanently discontinue Avelumab therapy Specialty consult	

Abbreviations: ACTH=adrenocorticotropic hormone; ADL = activities of daily living; ALT = alanine aminotransferase; AST = aspartate aminotransferase; BNP=B-type natriuretic peptide; CK-MB=creatine kinase MB; CT = computed tomography; FSH=follicle-stimulating hormone; GH=growth hormone; IGF-1=insulin-like growth factor 1; irAE = immune-related adverse event; IV=intravenous; LH=luteinizing hormone; MRI = magnetic resonance imaging; NCI-CTCAE = National Cancer Institute-Common Terminology Criteria for Adverse Event; PRL=prolactin; T4 = thyroxine; TSH = thyroid-stimulating hormone; ULN = upper limit of normal.

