
 • Transient (\leq 6 hours) Grade 3 flu-like symptoms or fever, which is controlled with medical management • Transient (\leq 24 hours) Grade 3 fatigue, local reactions, headache, nausea, emesis that resolves to Grade \leq 1 • Single laboratory values out of normal range that are unlikely related to study treatment according to the Investigator, do not have any clinical correlate, and resolve to Grade \leq 1 within 7 days with adequate medical management • Tumor flare phenomenon defined as local pain, irritation, or rash localized at sites of known or suspected tumor • Change in ECOG PS to \geq 3 that does not resolve to \leq 2 within 14 days (infusions should not be given on the following cycle, if the ECOG PS is \geq 3 on the day of study drug administration) • First occurrence of a Grade 3 IRR that meets conditions for continued therapy as outlined in Table 3.
Any Grade 2 AE should be managed as follows:

 • If a Grade 2 AE resolves to Grade \leq 1 by the last day of the current cycle, treatment may continue. • If a Grade 2 AE does not resolve to Grade \leq 1 by the last day of the current cycle, infusions should not be given on the following cycle. If at the end of the following cycle the event has not resolved to Grade 1, the patient should permanently discontinue treatment with a avelumab AE (except for hormone insufficiencies, that can be managed by replacement therapy; for these hormone insufficiencies, up to 2 subsequent doses may be omitted). • Upon the second occurrence of the same Grade 2 AE (except for IRR or hormone

insufficiencies that can be managed by replacement therapy) in the same patient, treatment with avelumab has to be permanently discontinued.

- Recurrent Grade 2 IRRs may not require treatment discontinuation and should be managed as outlined in Table 3

When a patient stops trial treatment an End of Treatment visit should be performed 28 days (+/- 5 days) after their last dose of avelumab. Assessments are to be performed as per section 7.3 and include:

- Physical Exam
- ECOG
- Vital signs
- Full blood count
- Biochemistry
- Hormone function
- Pregnancy test
- Urinalysis
- 12- lead ECG
- Disease assessment
- Adverse events

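### For a second Grade 2 immune-related event, Table 4 and Table 5 give incompatible avelumab instructions (clearly so for rash), and no text says which table prevails

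*Combined protocol and SAP*

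**What the plan says.** Section 7.5.4 gives short rules for treating immune-related events by grade, including "Grade 1 to 2 (persistent): manage similar to high grade AE (Grade 3 to 4", and then sends the reader to Table 4 for each organ system.

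The Table 4 row for Grade 1 to 2 rash covers recurrence directly. The trigger and action read "1 to 2 weeks or recurs: Withhold Avelumab therapy". After steroids are considered and tapered, the row ends "and resume avelumab therapy following steroids taper. If worsens: Treat as Grade 3 to 4".

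For Grade 2 diarrhoea or colitis the trigger is "5 to 7 days or recur: Treat as Grade 3 to 4". The Grade 3 to 4 row it leads to reads "Continue steroids until Grade 1, then taper over at least 1 month; resume Avelumab therapy following steroids taper (for initial Grade 3", and it stops avelumab for good at Grade 4 or at a recurrent Grade 3.

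Section 7.8 lists the circumstances in which treatment must stop, among them unacceptable toxicity, which it defines through Table 5. The Grade 2 part of Table 5 begins its recurrence rule "Upon the second occurrence of the same Grade 2 AE (except for IRR or hormone", completes the exception for insufficiencies manageable by replacement, and concludes "in the same patient, treatment with avelumab has to be permanently discontinued". For a Grade 2 event that lasts, Table 5 omits the next cycle's infusions if the event has not settled by the end of the current cycle. It stops avelumab permanently if the event is still unresolved when that next cycle ends.

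**The concern.** A site treating a second Grade 2 rash finds one instruction to re-dose after the taper and another never to re-dose. Following either departs from the other. With recruitment from 13 centres, the same event can be handled in opposite ways.

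Both errors carry a cost. Re-dosing exposes the patient again to a class of reaction that section 7.5.4 itself warns can be fatal. Stopping removes a drug that Table 4 would resume, in a disease where the protocol describes few good options.

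**Working it through.** No planned figure is at issue, so the check sets the two tables side by side and adds simple day counts.

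**Second occurrence of the same Grade 2 event**

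| Event | Table 4 (7.5.4) | Table 5 (7.8) | Conflict |
|---|---|---|---|
| Rash | Recurrence named: withhold, taper, resume | Permanent stop | Explicit |
| Renal | Withhold, taper, resume; no recurrence rule | Permanent stop | Through Table 4's silence |
| Other immune events | Withhold, taper, resume; recurrence stop written for Grade 3 only | Permanent stop | Through Table 4's silence |
| Diarrhoea or colitis | Handled as Grade 3 to 4: resume if counted as a first Grade 3, stop if counted as recurrent | Permanent stop | Only on the first reading |

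Table 5 does reach immune events. Its rule covers any Grade 2 event and exempts only infusion reactions and replaceable hormone insufficiencies. Table 4 manages the latter under its endocrine rows.

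**Lasting Grade 2 event under Other AEs**

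Inputs: 28-day cycles (7.2); a Table 5 limit at the end of the following cycle; a Table 4 limit of 12 weeks.

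- Table 5 limit for onset on cycle day d: 56 − d days after onset. For d = 1 this is 55 days; for d = 28 it is 28 days.
- Table 4 limit: 12 × 7 = 84 days.
- Distance between the limits: 84 − 55 = 29 days to 84 − 28 = 56 days.

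The distance matters only if the event resolves between the two limits. Example: onset on day 15 puts the Table 5 limit at 56 − 15 = 41 days. If the event settles at 45 days and the taper takes 30 days, Table 4 allows resumption at about 45 + 30 = 75 days, but Table 5 stopped avelumab at 41. Table 4 has a separate stop for more than 12 weeks of prednisone at 10 mg daily or above. It is not reached in this example, but it could close part of the window for later resolutions.

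**Lasting Grade 2 liver or lung event**

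The liver trigger is "5 to 7 days or worsens: Treat as Grade 3 to 4", and that higher row stops avelumab permanently. Lung does the same after 2 weeks without improvement. Table 5 merely permits treatment to go on if the event settles within the cycle. A site that stops complies with both tables, so there is no contradiction on duration. On recurrence these two Grade 2 rows are as silent as the renal row; the point does not rest on them.

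**Search for a precedence rule**

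- 7.2 refers to 7.5 for delays and modifications and does not rank it against 7.8.
- 7.5.4 points to Table 4 and does not mention Table 5.
- Table 5 points to Table 3 twice, for Grade 2 and Grade 3 infusion reactions, and to Table 4 not at all.

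The amendment log records that amendment 4 aligned Table 5 with Table 3. No equivalent link exists for immune events.

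**The case against.** The best defence is that the text already implies a ranking. Section 7.8 is mandatory in tone and its exemptions are listed by name, whereas Table 4 is introduced as guidance. On that reading a site manages and resumes under Table 4 unless a Table 5 stop is met. This has some force, but it is only a hint. The rash row expressly provides for recurrence followed by resumption, and if Table 5 always overrode it, that provision could never apply to a second Grade 2 rash. A safety instruction should not depend on the reader inferring a hierarchy.

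Three narrower objections stand and limit the point:

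- The gastrointestinal case is an ambiguity. If a recurrence counts as recurrent Grade 3, both tables stop.
- For a lasting event under Other AEs, Table 4 withholds avelumab until resolution and taper. It does not direct dosing up to 84 days, so the tables disagree only about events that resolve between the two limits.
- The general line on persistent Grade 1 to 2 events concerns treatment of the event and does not by itself show the defect. The table rows do.

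A reader might also infer that the tables clash in both directions because Table 4 is stricter for lasting liver and lung events. The documents do not support that, since Table 5 is permissive there.

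**Conclusion.** The inconsistency is real and narrow. It is explicit for a second Grade 2 rash. For second Grade 2 renal and other immune events it rests on reading Table 4's resumption rule as applying to recurrences, which nothing in those rows prevents. For diarrhoea or colitis it depends on counting the recurrence as a first Grade 3. The secondary conflict is confined to Grade 2 events under Other AEs that resolve after the Table 5 limit of 28 to 55 days but before 84 days.

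The number of patients affected cannot be stated. A reader might scale the 56 of 480 patients with potential autoimmune events in section 1.2.3 to this trial (30 × 56/480 = 3.5; 35 × 56/480 = 4.1) and call it a ceiling. It is an observed rate in solid-tumour cohorts. It does not bound the count here, and the share with recurrent Grade 2 events is not reported.

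Nor should a reader infer a flaw in the statistical design. The response-rate analysis, the interim rule and the sample size do not depend on which table is followed. This is a drafting inconsistency with a patient-safety consequence, and it should be corrected.

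**What to change.** Add one precedence sentence to the Grade 2 part of Table 5, modelled on its existing reference to Table 3. The documents do not settle which table is clinically right, so the chief investigator and the Trial Safety Committee should choose between:

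- **Table 4 governs.** Add to Table 5: *Grade 2 immune-related AEs, including recurrences, are handled according to Table 4.* This keeps the stricter liver and lung stops. The gastrointestinal row should then say whether a recurrent Grade 2 counts as a first or a recurrent Grade 3.
- **Table 5 governs.** Add to Table 4: *Resumption after a Grade 2 event does not apply on a second occurrence, or once the Table 5 time limit has passed.* The Table 5 exceptions for infusion reactions and replaceable hormone insufficiencies stay as they are.

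The cost is a sentence or two in the next amendment and a notice to sites. Sample size, visit schedule and analysis do not change.
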